1.4.2. Exclusion Criteria

- 1.4.2.1. The patient cannot be undergoing chemotherapy at the time of enrollment unless it is post-transplant maintenance chemotherapy. Patients undergoing post-transplant maintenance chemotherapy are permitted to enroll.
- 1.4.2.2. The patient must have no evidence of disease progression or recurrence. Specifically, for the prostate cancer population, the patient must have no evidence of disease progression on their current ADT regimen at the time of enrollment.
- 1.4.2.3. The patient must not be a night shift worker, where night shift is defined as working a significant number of hours (i.e. more than half) between the hours of 11PM and 6AM on a regular basis.

1.5. *Intervention Plan*

- 1.5.1. Participants will be consented, enrolled, and randomized remotely with a Research Coordinator prior to beginning the trial. A review of inclusion/exclusion criteria will be conducted to determine the patient's eligibility for enrollment. Study procedures will be reviewed with the patient, and documentation of informed consent will be obtained. After signing the informed consent form (ICF) either in person or electronically using SignNow or other process approved by the University of Michigan IRBMED, patients will be assigned a unique study ID number in sequential order. Those who are found to be ineligible will be replaced.
- 1.5.2. After providing informed consent, the participant will be provided, in the clinic or via mail, a wearable device and a pair of glasses, which will be either blue-blocking (intervention group) or clear (control group). Both of these are described in detail in **Appendix A**. When both are in the participant's possession, the study coordinator will schedule a second meeting with the participant to onboard them to the specifics of the study.

- 1.5.3. The study coordinator will walk the participant through setting up the app and entering their Research ID number. They will ensure that the participant is able to connect to the wearable device via their phone and will explain to the subject that they should not wear the blue-blocking glasses while driving or if their vision will be impaired by them in a way that challenges their mobility.
- 1.5.4. Participants will be allowed to use sleep aids over the course of the trial. There will be no restriction on their usage; however, subjects will be asked to report on a weekly basis what sleep aids they consumed, as well as the number of alcoholic drinks they consumed. This survey will be carried out in the app.
- 1.5.5. Once the trial has begun, study coordinators will track completion of surveys, and in the event of missing data will follow-up with subjects to assess challenges to encourage survey completion. SYNC software will be maintained in collaboration with Arcascope, Inc. After randomization, subjects will complete baseline assessments, as outlined in the metrics Appendix. They will be asked to wear the wearable device day and night for twelve weeks. During this time, the app will deliver ecological momentary assessments of fatigue daily at random times of day and the validated 4-item PROMIS Fatigue questionnaire weekly to both the control and interventional groups. At the end of the twelve-week period, the subjects will remotely complete end-of-trial assessments.
- 1.5.6. Intervention arm (SYNC app): Participants randomized to the intervention arm will be instructed on how to download the app on their mobile phones (iOS) and how to operate the wearable device. The app will record when the user opens the app, as well as when they check off having completed an assigned task; e.g. “getting bright light exposure”. Please see **Appendix A** to view the components of the wearable device. Please see **Appendix B** to view specifications of the mobile app. Any PHI information will be stored on University of Michigan servers in a secure way. Only non-PHI information will be stored and collected via the Sync app. The SYNC will be downloaded onto patient mobile phones and can be used freely throughout the intervention period because it contains no PHI data.
- 1.5.7. Control arm: Participants randomized to the control arm will be instructed on how to download the SYNC app and how to operate the wearable sensor. Their research ID will trigger the “control” recommendations from SYNC, which are chosen to minimize circadian effect. Any PHI information will be stored on University of Michigan servers in a secure way. Only non-PHI information will be stored and collected via the Sync app. The SYNC will be downloaded onto patient mobile phones and can be used freely throughout the intervention period because it contains no PHI data.
- 1.5.8. Light-blocking and “dummy” glasses: Participants will be provided either blue-blocking glasses (intervention group) or clear glasses that do not block visible light (control). The blue-blocking glasses are meant to reduce the circadian effect of light at certain times for participants. Both pairs of glasses will be capable of being worn over regular glasses for vision impairment. Participants will be informed not to wear the glasses while driving, or when doing motor activity that risks injury with vision impairment. They will also be informed that they are not required to wear the glasses if doing so makes them feel uncomfortable; e.g. if they are out in public.
- 1.5.9. Wearable sensor device: Each participant will be given a wearable sensor to wear throughout the treatment period, except while in water or when charging. The goal is to collect objective, continuous, multi-parameter physiological data (e.g., total

hours of sleep, sleep quality, total number of steps) on patients throughout the treatment period to correlate with their subjective, snapshot participant-reported outcomes collected over the course of the trial. The de-identified wearable data will be stored on servers purchased by the small business partner, Arcascope. For troubleshooting, detailed instructions will be provided for all participants, and customer support will be available 8AM – 5PM CST. Our team is available by pager after hours, if needed.

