5. STATISTICAL CONSIDERATIONS

- 5.1. *Study Design.* The clinical trial is a two-arm randomized controlled trial. After completion of the intervention, data analysis will be conducted according to the statistical analysis plan outlined below. Descriptive statistics will be performed prior to conducting the statistical analyses. An intention-to-treat (ITT) analysis of the results will be based on the initial assignment of the randomized participants. With the ITT approach, participants will be analyzed according to the treatment assignment, even if the participant drops out of the study. The ITT approach minimizes biased comparisons among the treatment arms. Missing data will be imputed using the last collected data from the subject prior to dropout.
- 5.2. *Accrual.* It is estimated that 18-months will be necessary to enroll the targeted sample size. Accrual will be reported by race, ethnicity, gender, and age.
- 5.3. *Study Duration.* Survey results and wearable data will be actively collected from participants over the course of 12 weeks. At the conclusion of the 12 weeks, passive collection of wearable data through the app will continue for up to one year for each participant who opts-in to continue using the app. Medical records may be accessed for up to five years after the conclusion of the 12-week collection period.
- 5.4. *Randomization.* Blocked randomization will be used to limit bias and achieve an equal distribution of participants to the intervention and control arms of the study (69 randomized, 69; with 23 from each cancer population in each arm). This approach will recruit participants in small blocks to ensure that half of the participants within each block will be allocated to the treatment and the other half to the control. The size of the blocks will be permuted to limit selection bias, and within each block, the order of patients will be random. The study statistician will create a randomization list before the study begins enrollment using the statistical package R. This list will be used by the study group in assigning patients to the correct study arm.
- 5.5. *Blinding.* Study arm assignments cannot be blinded to the investigators or the rest of the study team because it will be known whether participants have SYNC on their mobile device or not (due to technical purposes).

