1. Reliability: The degree to which a measure is free of error. It can be estimated by the internal consistency of the responses to the measure, or by correlating total scores on the measure from two time points when there has been no true change in what is being measured (for z-scores, reliability = $1 - SE^2$).
2. Precision: The consistency of the estimated score (reciprocal of error variance).
3. Information: The precision of an item or multiple items at different levels of the underlying continuum (for z-scores, information = $1/SE^2$).
4. Standard Error (SE): The possible range of the actual final score based upon the scaled T-score. For example, with a T-score of 52 and a SE of 2, the 95% confidence interval around the actual final score ranges from 48.1 to 55.9 ($T\text{-score} \pm (1.96 \times SE) = 52 \pm (1.96 \times 2) = 48.1 \text{ to } 55.9$)

The final score is represented by the T-score, a standardized score with a mean of 50 and a standard deviation of 10 points.

5.9. *Interim Analysis*. There will be no interim analyses for efficacy or futility for this trial.

5.10. *Patient Characteristics*. Patient characteristics will be summarized for all participants. Patient characteristics to be examined may include: age, gender, race/ethnicity, treatment and pathology information (including dates), and clinical outcomes; e.g. survival, relapse, and toxicities.

5.11. *Analysis Populations and General Analysis Guidelines*.

5.11.1. Primary Analysis Population. All participants enrolled, consented, and completing at least the baseline outcome measures will be included in the primary analysis population. Analyses for the primary and secondary endpoints will use the primary analysis population: The primary analysis will occur once all patients have been followed for the duration of the 12-week trial, data adjudication completed, and data are locked.

5.11.2. General Analysis Guidelines. Primary analyses for the primary, secondary, and exploratory endpoints will use the primary analysis population. Analyses of each endpoint in each population will follow the

analysis plans, as described below. We expect minimal missing data (<5%) for the primary endpoint and secondary endpoints based on past experience with mobile app studies.

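### Baseline surveys follow randomization and receipt of arm-specific glasses, and two rules then exclude randomized patients from analysis, contradicting intention to treat

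*Combined protocol and SAP*

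**What the plan says.** **Order of events.** Section 1.5.1: "Participants will be consented, enrolled, and randomized remotely with a Research Coordinator prior to beginning the trial". Section 1.5.2 then has each patient receive "a pair of glasses, which will be either blue-blocking (intervention group) or clear (control group"), in clinic or by mail, together with the wearable. The next step is conditional on delivery: "When both are in the participant's possession, the study coordinator will schedule a second meeting with the participant to onboard them". At that meeting the app is installed and the Research ID entered (1.5.3), and the Synopsis says this ID decides which app version loads. Section 1.5.5: "After randomization, subjects will complete baseline assessments". Section 4.3 has the baseline surveys answered in the SYNC app and calls them pre-intervention. The Time and Events Table puts them on the first day of the trial.

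**Who is analysed.** Section 5.11.1: "All participants enrolled, consented, and completing at least the baseline outcome measures will be included in the primary analysis population". Section 4.7.1 says patients who decline the wearable are replaced and left out of the analysis. Against this, 5.1 says "participants will be analyzed according to the treatment assignment, even if the participant drops out of the study", and 5.12 describes an intention-to-treat analysis of every participant.

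**How it is analysed.** Section 5.12 compares end-of-trial means by a two-sample t-test or Wilcoxon test, with regression as a complement. Section 5.1 fills missing values with the last value collected. Section 1.3.2 defines the secondary objective as change from baseline to week 12.

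**The concern.** Completing baseline is itself a post-randomization event, and so is accepting the wearable. If either depends on arm, the groups compared are no longer the groups randomized, and the primary comparison loses the protection of randomization. A patient lost between randomization and onboarding is in the analysis under 5.12 and out of it under 5.11.1. The plan therefore does not fix its own denominator.

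A second route runs through the baseline value. It is self-reported after a patient has received orange or clear lenses (Appendix A) and loaded the arm's app. If answers shift by arm, a change score or a baseline-adjusted estimate absorbs the shift.

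**Working it through.** **1. The order.** No single sentence puts baseline after the glasses. It follows from four steps: randomization (1.5.1); glasses and wearable in hand (1.5.2); app set-up with the arm-determining ID (1.5.3, Synopsis); baseline after randomization and inside that app (1.5.5, 4.3). A survey in an app that is installed only after the glasses arrive cannot precede the glasses.

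**2. The plan's own figure.** Section 5.7 has effect 0.5 SD, two-sided alpha 0.05, power 0.80, 64 per arm. A two-sample t calculation gives n = 63.8, rounded up to 64, with power 0.801. Allowing for 7% dropout: 64 / 0.93 = 68.8, so 69 per arm and 138 in total. The figure reproduces. It leaves no room for baseline non-completion on top of dropout: if 67, 64 or 60 of 69 per arm complete baseline and 7% then drop out, power is about 0.79, 0.77 or 0.74.

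**3. Inclusion route (reaches the primary test).** Suppose m of 69 patients are excluded in one arm only, and their outcomes differ from the remaining patients' by D SD. The full-arm mean differs from the analysed mean by (m/69) x D. Both m and D are assumed.

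| m of 69 | D = 0.5 | D = 1.0 | Share of 0.5 SD |
|---|---|---|---|
| 3 | 0.022 | 0.043 | 4%-9% |
| 5 | 0.036 | 0.072 | 7%-14% |
| 7 | 0.051 | 0.101 | 10%-20% |
| 10 | 0.072 | 0.145 | 14%-29% |

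For scale, 5% of 69 is 3.5 patients. The missing-data rate expected in 5.11.2, if it also described baseline non-completion, would sit near the top row. If 5% of all 138 (about 7) fell in one arm, the third row applies.

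With 64 per arm, the standard error of the difference is sqrt(2/64) = 0.177 SD. Under no true effect, a shift of 0.07 SD raises two-sided type I error from 0.05 to about 0.07, and 0.14 SD raises it to about 0.12.

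**4. Baseline-value route.** Let b be an assumed arm-related shift in reported baseline.
- Change score: the bias is b in full.
- Baseline-adjusted regression: the bias is slope x b. With slope 0.5-0.7 and b = 0.1-0.2 SD, this is 0.5 x 0.1 = 0.05 to 0.7 x 0.2 = 0.14 SD.
- Unadjusted end-of-trial t-test: b enters only through carried-forward values. Even if all 7% of dropouts carried a baseline value, b = 0.1-0.3 SD moves the mean by 0.07 x b = 0.007-0.021 SD.
- Secondary PROMIS forms are collected only on the first and last day, so every dropout's carried-forward score is the post-allocation baseline.

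**The case against.** **Baseline is called pre-intervention (4.3).** This stands in part. It keeps the answers ahead of following the app's recommendations, but it does not place them ahead of allocation or receipt of the glasses.

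**Loss may be rare and balanced.** Coordinators hold an onboarding meeting, track surveys and chase missing data (1.5.5), and 5.11.2 expects under 5% missing. The wearable does not differ by arm. Nothing in the documents shows that non-completion would differ by arm. This stands as a limit on size. It does not remove the contradiction between 5.11.1 and 4.7.1 on one side and 5.1 and 5.12 on the other.

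**Patients may not know their arm.** A reader might infer that patients given clear lenses know they are controls, and leave or answer differently out of disappointment. The documents do not say so. Control patients get their own glasses, app and recommendations, and 5.5 speaks only of staff being unblinded. The lenses do look different, and no section states that participants are blinded, so knowledge of arm is possible but not shown.

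**The primary test needs no baseline value.** This stands. A reader might take the 0.05-0.14 SD (10%-28% of the target) in the regression example as bias in the primary result. It is not: 5.12 tests unadjusted end-of-trial means, and its example covariates do not include baseline fatigue. Nor is the direction fixed. If optimism lowered reported baseline fatigue in the intervention arm, adjustment would make the benefit look smaller.

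**Conclusion.** The point holds on order and on population. Baseline follows randomization and receipt of arm-specific glasses, and 5.11.1 and 4.7.1 create post-randomization exclusions that contradict 5.1 and 5.12. That conflict needs resolving whatever the size of the bias.

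The exclusion route is the one that reaches the primary comparison. Its size, about 0.02-0.14 SD, rests on assumed one-sided losses of 3-10 of 69 and an assumed outcome difference of 0.5-1.0 SD. It may run in either direction, and is probably near the lower end if losses are as few as the plan expects. The baseline-value route is a matter for the secondary change objective, carried-forward values and optional baseline-adjusted models. The documents do not support reading this as a demonstrated bias in favour of SYNC.

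**What to change.** **Timing (1.5.1-1.5.5 and 4.3).** Collect all baseline PROMIS forms, including Fatigue 4a, after consent and confirmed eligibility, but before the arm is assigned or revealed and before glasses are issued. Keep the interval to the first trial day short, because the fatigue, sleep, anxiety and depression forms ask about the past 7 days. The fatigue rating used for eligibility (1.4.1.6) already precedes allocation, so the contact exists.

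**Population (5.11.1 and 4.7.1).** Define the primary population as all randomized participants by assigned arm. Wearable decliners stay in the analysis.

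**Missing data (5.1).** Replace the last-value rule, since it has nothing suitable to carry forward for a patient with no post-randomization data. Either a likelihood-based mixed model on the weekly Fatigue 4a scores, with the pre-allocation baseline in the response, or multiple imputation would serve.

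**Cost.** Sample size stays at 69 per arm, with no extra visits. The price is a form outside the app, so baseline and exit surveys differ in mode, and a baseline taken slightly before trial start. If enrolment has already begun, the population and missing-data changes can still be made before data lock. For patients already enrolled under the current order, the baseline should be reported as post-allocation.

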3. STUDY ENDPOINTS

3.1. *Primary Endpoint.* The primary endpoint is **fatigue**, as assessed by a daily fatigue questionnaire and a weekly 4-item PROMIS fatigue questionnaire.

3.2. *Secondary Endpoint.* The secondary endpoints are sleep disturbance, anxiety, depression, physical function and global health, as measured via the following PROMIS validated instruments:

- PROMIS Sleep Disturbance (8-item)
- PROMIS Anxiety (7-item)
- PROMIS Depression (8-item)
- PROMIS Physical Function (8-item)
- PROMIS Global Health (10-item)

3.3. *Exploratory Endpoints.*

3.3.1. Activity data. Patient activity (steps) and sleep will be measured continuously from the start to the end of the trial through wearable sensors.

3.3.2. Health care utilization data. Patient health care utilization data (e.g., total count of hospital days, emergency department visits, readmissions, and ambulatory care clinic visits) will be captured through the electronic health record as well as self-report (i.e., if the patient is readmitted at an outside hospital other than Michigan Medicine).

3.3.3. Sleep aid utilization data will be collected via self-report in the app once a week.

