A RANDOMIZED TRIAL OF THE SYNC APP

Protocol Number: UMCC 2020.157

National Clinical Trial (NCT) Identifier: NCT04827446

Principal Investigator: [name] [name], MS
[name]
[name]
[contact]
[contact]
Email: [contact]

Co-Investigators: [name] PhD, [name] MD PhD, [name]
MD, [name] PhD, [name] MD PhD

Biostatistician: [name] PhD
[contact]
Email: [contact]

Single Center: University of Michigan

Version: April 4, 2022

Table of Contents

PROTOCOL SYNOPSIS	3
STUDY SCHEMA: SCHEDULE OF EVENTS	6
TIME AND EVENTS TABLE	7
INTERVENTION ARM VS CONTROL ARM	8
1. BACKGROUND AND SIGNIFICANCE	9
2. STUDY DESIGN	13
3. STUDY ENDPOINTS	17
4. PATIENT ENROLLMENT AND EVALUATION	18
5. STATISTICAL CONSIDERATIONS	20
APPENDIX A: DESCRIPTION OF DEVICES	23
Fitbit Charge 3	30
Apple Watch	36
APPENDIX B: SYNC COMPONENTS	51
APPENDIX C: USER-REPORTED OUTCOME MEASURES	62
APPENDIX D: REFERENCES	60

PROTOCOL SYNOPSIS

A RANDOMIZED TRIAL OF THE SYNC APP

Principal Investigator: [name]

Study Design: This is a study to assess whether individually tailored lighting and behavioral interventions delivered through an app are able to reduce symptoms of fatigue and improve quality of life across three populations of cancer patients. We will recruit 138 patients (69 control, 69 interventional) across three cancer populations: breast cancer and prostate cancer, and patients who have undergone hematopoietic stem cell transplant (HSCT). Participants will be randomized 1:1 to either the interventional SYNC app or to a control app.

Primary Objective: The primary objective is to test the statistical significance or difference between the intervention arm and the control arm in the measured outcome of fatigue, as quantified by daily fatigue surveys and weekly PROMIS Short Form v. 1.0 Fatigue 4a surveys.

Secondary Objective: The secondary objective will be to assess user sleep disturbances, anxiety, depression, physical function, and global health via a suite of PROMIS questionnaires.

Exploratory Objectives: Exploratory objectives will be to assess: i) physical activity through physiological data capture using the wearable sensor; ii) health care utilization (i.e., total count of hospital days, ED visits, readmissions, and ambulatory care clinic visits), and iii) sleep aid usage, as measured by self-report.

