1. STUDY DESIGN

- 1.1. *Study Overview.* This study will use a two-arm randomized study design. Participants will be recruited across three cancer types. Each of the participants will be randomized to an active “intervention” arm (using the full SYNC app) or to a control arm (using a “dummy” version of the SYNC app that gives recommendations for light at times that should not significantly affect the circadian clock). The random allocation of participants to the treatment arm or control arm establishes the basis for testing the statistical significance or difference between the groups in the measured outcome (patient fatigue, assessed by a daily 1-question fatigue survey and the PROMIS 4-item Fatigue). Patient age, gender, and other prognostic baseline characteristics that could potentially confound an observed association, including those that are unknown or unmeasured, will be distributed equally, except through chance alone, through random assignment. Thus, this design is well-suited to our goal of assessing the efficacy of a mobile health intervention, SYNC, on participants.
- 1.2. *Primary Hypothesis.* The primary hypothesis is that a mobile-app delivered circadian intervention (SYNC) will reduce patient fatigue.
- 1.3. *Study Objectives*
 - 1.3.1. Primary Objective. To test the difference between the “intervention” (full SYNC app) arm and the control (limited SYNC app) arm in the measured outcome of patient fatigue, assessed by daily 1 question surveys and weekly 4-item PROMIS questionnaires over the course of 12 weeks.
 - 1.3.2. Secondary Objective. To determine the change in sleep disturbances, anxiety, depression, physical functioning, and global health through PROMIS questionnaires, between baseline and the 12-week assessment in both the control and intervention arms, and to look for differences in this change between the two arms.
 - 1.3.3. Exploratory Objectives
 - 1.3.3.1. Change in patient physical activity through physiological data capture using the wearable sensors in the control versus intervention arm.
 - 1.3.3.2. Change in patient health care utilization (e.g., total count of hospital days, readmissions, and ambulatory care clinic visits) in the control versus intervention arm
 - 1.3.3.3. Change in patient sleep aid usage in the control versus intervention arm.
- 1.4. *Participant Eligibility*
 - 1.4.1. Inclusion Criteria

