- 5.6. *Primary Endpoint.* The primary objective of the study is to test the effects of SYNC in a randomized controlled clinical trial design. Patients will be randomly assigned to the treatment arm or the control arm. The primary objective is to quantify the effects of the light interventions delivered by SYNC on patient fatigue.
- 5.7. *Sample Size Considerations.* We will enroll 138 cancer patients, with half in the intervention arm and half in the control arm. Our primary endpoint is the PROMIS 4-item Fatigue Short Form. The age- and sex-adjusted norm for the Fatigue scale is 50 points, with a standard deviation of 10 points. These statistics have been shown to be largely generalizable to the cancer patient population (mean: 52, standard deviation 7.6). Our study will have power of 0.80, assuming a two-sided Type I error rate of 0.05, to detect an effect size of half the standard deviation between the intervention and control arms if 64 cancer patients are enrolled in each of the control and intervention groups. A mean difference of one-half a standard deviation is clinically meaningful and is considered a medium effect size for clinical trials. During the primary analysis, we will adjust for the fact

that there are three cancer populations in our data and will look for a well-defined effect that is marginal within each population. We will accrue a total of 69 patients in each arm to account for attrition of data, assuming a 7% dropout rate from the trial.

5.8. PROMIS® measures use Item Response Theory (IRT), a family of statistical models that link individual questions to a presumed underlying trait or concept of global health represented by all items in the scale. PROMIS® instruments are scored using item-level calibrations. The most accurate way to score a PROMIS® instrument is to use the Health Measures Scoring Service, which our Study Team has experience with. This method of scoring uses “response pattern scoring,” which uses responses to each item for each participant. Response pattern scoring is especially useful when there is missing data (i.e., a respondent skipped an item), or different groups of participants responded to different items).

There are four key features of the score for PROMIS® Fatigue:

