5.12. *Analysis of Primary Endpoint.* Analysis will be an intent-to-treat analysis that includes all participants. Mean Global Health scores at the end of the trial will be compared using a two-sample *t*-test (or Wilcoxon Rank Sum test if non-normality is apparent) with a significance level of 0.05. Linear regression models will be performed to complement the results of the *t*-test and adjust for specific baseline participant's characteristics (e.g., demographic, social, environmental) to increase the precision of our inference. There is a possibility that patient characteristics will be unbalanced since our randomization scheme will be applied to participants. Thus, our models also will assess potential moderating or mediating effects.

5.13. *Analysis of Secondary Endpoint.*

Mean PROMIS scores (PROMIS sleep disturbances, anxiety, depression, physical function, and global health) for each arm at the end of the trial will be compared using a two-sample *t*-test (or Wilcoxon Rank Sum test if non-normality is apparent) with a significance level of 0.05. Linear regression models will be performed to complement the results of the *t*-test and adjust for specific baseline participant's characteristics (e.g., demographic, social, environmental) to increase the precision of our inference. There is a possibility that patient characteristics will be unbalanced since our randomization scheme will be applied to participants. Thus, our models also will assess potential moderating or mediating effects.

5.14. *Analysis of Exploratory Endpoints.*

5.14.1. Patient activity. The accelerometer data of each subject will be transformed into a low-dimensional representation using motif discovery algorithms.⁷⁹ Such techniques are completely data-driven, and search for motifs (i.e., patterns) in the data that occur more often than chance. A signal can then be represented by the number of times a particular motif occurs. Others have successfully used such techniques for representing a variety of waveform data, including accelerometer and continuous glucose data.⁸⁰⁻⁸² The accelerometer data will be processed to derive estimates of total sleep duration (i.e., hours per night), wake after sleep onset, and sleep efficiency (i.e., ratio of sleep to wake). The variables will be compared between arms.

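### Primary fatigue is defined on two instruments, sized on one and tested on neither, and no rule says whether either or both must succeed

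*Combined protocol and SAP*

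**What the plan says.** The combined protocol and SAP gives three different accounts of the primary variable.

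- **Two instruments.** Section 3.1 defines primary fatigue "as assessed by a daily fatigue questionnaire and a weekly 4-item PROMIS fatigue questionnaire". Objective 1.3.1 in the Study Design section has it "assessed by daily 1 question surveys and weekly 4-item PROMIS questionnaires over the course of 12 weeks", and the synopsis objective "as quantified by daily fatigue surveys and weekly PROMIS Short Form v. 1.0 Fatigue 4a surveys". The study overview (Study Design 1.1) also names both.
- **One instrument.** Section 5.7, and the accrual objective in the synopsis, state: "Our primary endpoint is the PROMIS 4-item Fatigue Short Form". The power statement there concerns that form only.
- **Neither instrument.** Section 5.12, headed as the analysis of the primary endpoint, says: "Mean Global Health scores at the end of the trial will be compared using a two-sample" *t*-test (or a rank-sum test), "with a significance level of 0.05". Section 3.2 lists Global Health as secondary, and 5.13 tests it again as such.

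Section 5.6 speaks of patient fatigue without naming an instrument. The analyses in 5.13 cover five other PROMIS scales, and those in 5.14 cover activity, utilization and sleep aids. The daily item is sent at random times of day for 12 weeks (Study Design 1.5.5) and has four response categories (Appendix C). Section 5 gives it no summary measure, time point, model or test. No section states a multiplicity rule, a ranking of the instruments or a split of the 0.05.

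**The concern.** A primary claim needs one variable, one time point and one decision rule fixed in advance. Here a reader can find support in the text for the daily item, the weekly form, or both together, and the section that should settle the matter tests something else. The two plausible ways of using both instruments have different operating characteristics, and each breaks one of the two figures on which the design rests: the 0.05 error rate or the 0.80 power. Section 5.5 says that the study team is not blinded to arm. Without a fixed rule, the instrument, summary and time point that carry the claim could be settled after results are known and still be defended from protocol wording.

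**Working it through.** **Inputs from the documents.** Section 5.7: "Our study will have power of 0.80, assuming a two-sided Type I error rate of 0.05"; a difference of 0.5 SD between the arms; 64 evaluable per arm, 7% dropout, 69 enrolled per arm. Section 5.12: a single level of 0.05.

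**Inputs assumed.** The correlation r between the two test statistics is not given, so a range of 0 to 0.9 is used. For joint power, a true effect of 0.5 SD is assumed on both instruments.

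**Step 1: the plan's own figure.** Normal approximation: n = 2(1.960 + 0.842)² / 0.5² = 62.8, so 63 per arm. The t-test calculation gives 63.77, so 64. With 64 per arm the expected test statistic is 0.5 × √(64/2) = 2.828, and power is Φ(2.828 − 1.960) = 0.807 (0.801 by the t-test). Dropout: 64 / 0.93 = 68.8, so 69. The stated sample size reproduces for one endpoint tested once at 0.05.

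**Step 2: either instrument suffices.** With no effect on either, and each tested at two-sided 0.05, the chance of at least one rejection at r = 0 is 1 − 0.95² = 0.0975. For r > 0 it is 1 − P(|Z₁| < 1.960 and |Z₂| < 1.960) under a bivariate normal.

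**Step 3: both must succeed.** Joint power is P(Z₁ > 1.960 and Z₂ > 1.960), each Z having mean 2.828. At r = 0 this is 0.807² = 0.652.

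| Assumed r | Either suffices: familywise error | Both required: power at 64 per arm |
|---|---|---|
| 0 | 0.0975 | 0.65 |
| 0.7 | 0.083 | 0.72 |
| 0.9 | 0.070 | 0.76 |

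Counting only false wins in the favourable direction, the either-or error is 0.049, 0.042 and 0.035 at the same correlations, against a nominal 0.025. Under the both-required rule, with no effect on either instrument, the two-sided joint rejection rate is 0.0025, 0.017 and 0.030.

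**Step 4: splitting the level.** At 0.025 for each instrument, power per instrument at 64 per arm is 0.71 (t-test). Restoring 0.80 needs 78 evaluable per arm; 78 / 0.93 = 83.9, so 84 enrolled per arm and 168 in total, against the planned 138.

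**Step 5: single primary.** PROMIS Fatigue 4a alone at 0.05 is the case in Step 1: 64 evaluable and 69 enrolled per arm, unchanged.

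**The case against.** The best defence is that the plan does commit to one endpoint. Section 5.7 and the synopsis accrual text use the singular and name PROMIS Fatigue 4a, 5.12 plans a single comparison at 0.05, and power is claimed for the PROMIS form only. A reader might infer from 3.1 that the trial gives itself two chances to win and so runs at close to 10% error. The documents do not support that: nowhere do they say that success on either instrument is enough, and no test of the daily item is planned. The figures in Step 2 apply only if an either-or rule were adopted, and r = 0 is an upper limit that is hard to credit for two self-reports of fatigue by the same person. This part of the defence stands.

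It does not remove the contradiction. Section 3.1 is the formal endpoint definition, three other places agree with it, and 5.7 neither ranks the instruments nor withdraws the daily one. Section 5.12 cannot break the tie because it names neither.

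A reader might also infer that only the daily series lacks an analysis. That is too narrow: the weekly PROMIS form has no named test either, nor a rule for which weekly score counts.

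Demoting the daily item is not the only remedy. A both-required rule, a ranked order or a split level would also settle the matter, but the first and last have the power or sample-size costs shown above.

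**Conclusion.** The concern holds as an unresolved contradiction with a missing decision rule, not as a demonstrated inflation of error. Two instruments are primary in four places, one in two places, and a third variable is tested in the primary analysis.

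The consequence depends on how the gap is filled. An either-or rule would put the familywise error at about 7.0% to 9.75%. A both-required rule would not raise the error above 5% but would cut power to about 0.65 to 0.76. Both ranges rest on assumed correlations of 0 to 0.9 and the normal approximation; the power range also assumes a 0.5 SD effect on both instruments. A single primary on PROMIS Fatigue 4a delivers the stated 0.05 and 0.80 with the planned numbers. That the text disagrees with itself, and that neither fatigue instrument has a named primary test, needs no assumption.

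**What to change.** 1. In the synopsis objective, the study overview, objective 1.3.1 and section 3.1, name the PROMIS Fatigue 4a T-score at the end of the 12-week trial as the single primary endpoint, tested at two-sided 0.05. This matches 5.7 and the synopsis accrual text.
2. In 5.12, replace Global Health with that score. Without this step the newly named sole primary would still have no test. Global Health remains covered by 5.13.
3. List the daily item as secondary and add a short analysis to section 5: an ordinal or linear mixed model over the roughly 84 daily responses per participant (12 weeks × 7 days).

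The cost is wording in five places plus one added analysis paragraph, with no change to data collection or sample size. The daily item can then no longer carry the primary claim. If the team wants it to, the plan must instead state the rule and accept the power or sample-size cost of that rule.
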